COVID-19 diagnostics for Africa

Protocol Number:

Version Number: 1.00

Date: 20.12.2020

Confidentiality Statement: This document contains confidential information that cannot be disclosed to anyone other than the recipient study staff, advisors to the project, and members of the Institutional Review Board/Institutional Ethics Committee. This information cannot be used for any other purpose than the evaluation or conduct of the clinical investigation without the prior written consent.

Protocol: AfriDx Version: 1.0 20 December 2020

Contents

COVID-19 diagnostics for Africa	1
Protocol Number:	1
Version Number: 1.00	1
Date: 20.12.2020	1
1.0 Background and rationale for the study	5
2.0 Aim and study objectives	6
3.0 Study design	7
4.0 Research participants	8
5.0 Study procedures	8
6.0 Recruitment	12
7.0 Consent process	12
8.0 Risks	12
9.0 Mitigation of risks	12
10.0 Benefits	12
11.0 Study and safety monitoring	13
12.0 Managing and reporting adverse events	13
13.0 Managing and reporting unanticipated problems or protocol deviations	13
14.0 Confidentiality and data management	13
15.0 Study costs	14
16.0 Care for injury	14
17.0 Compensation	14
18.0 References	14

Protocol Summary

Title	COVID-19 diagnostics for Africa								
Aim	The aim of the project is to provide reliable diagnostic systems for the confirmation of the clinical diagnosis of COVID-19 in Africa from first infection through to recovery and immunity.								
Study Design	This study is a cross sectional experimental which involves the development and evaluation of two low cost point of care (POC) and rapid throughput NAT and SARS-Cov-2 antibody titre tests. This study has been organised into 9 work packages under the broad themes: Project management, development of point of care diagnostics, clinical study and field test, innovation and dissemination.								
Samples details	Nose, throat or nasopharyngeal swab, sputum or bronco-alveolar lavage will be collected for diagnostic testing and the Essential Information for Clinical Studies form. Sera from SARS-Cov-2 positive and negative patients will be used to validate a proof of concept Immunoassay.								
Number & Name of Site(s):	 Three sites. Kumasi Centre for Collaborative Research in Tropical Medicine (KCCR), Ghana Noguchi Memorial Institute for Medical Research (NMIMR) Kwame Nkrumah Universitry of Science and Technology (KNUST) 								
Study Duration:	Fifteen months (approx.).								
Description of Device:	The total setup consists of innovative portable and price-competitive POC RT- LAMP (PATHPOD from DTU, a novel raw material production process for low resource countries and a proof of concept immunoassay (UCAM) PATHPOD: Nucleic acid test for viral RNA, which uses RT-LAMP (reverse transcription loop-mediated amplification). The PATHPOD system consists of an instrument with integrated heater, optical detection systems, and polymeric injection moulded Lab-on-a-chip cartridges with 12 chambers suitable for on line or on-site rapid detection of detect COVID-19 virus in clinical, environmental and animal samples. The prototype chip with 10 samples and 2 controls is made in a low-cost polymeric material by injection moulding. It can easily be up-scaled for industrial production. The industrial version of the chip can include 32 samples. The PATHPOD Lab-on-a-chip (LOC) system includes integrated sample preparation and real-time reverse transcriptase (rRT) Loop-mediated Isothermal Amplification (LAMP) for rapid and quantitative detection of COVID-19 virus.								
Objectives:	Primary Objective:								

	1.To provide reliable diagnostic systems for the confirmation of the clini diagnosis of COVID-19 in Africa from first infection through to recovery a immunity									
	Specific Objectives:									
	1.1. To use the front line testing facilities in NMIMR and KCCR, Gham testbed for a new POC nucleic acid diagnostic emerging from DTU (PAT - detection of virus RNA).									
	Secondary Objective :									
	1. To replace the BST and RT enzymes in the PATHPOD with BST and									
	RT constructs designed by UCAM for low resource production in									
	Africa and evaluate the AfriDX-RT-LAMP alongside the PATHPOD and									
	standard RT-qPCR procedure.									
	4. To develop an Antibody Titre assay to proof of principle from a UCAM									
	single-chain antibody (scFv) library and produce scFv constructs for									
	low resource production of a lateral flow immunoassay (LFIA) in									
	Africa (AfriMx).									
	5. To evaluate combined batch testing as methodology adopted from									
	normal veterinary protocols (but not widely used for human testing)									
	and assess accuracy, cost and time benefits in epidemic testing									
	pathways.									
	6. To draft a plan to produce AfriDx in Africa for the African market, with									
	outline analysis of socioeconomic and healthcare benefits.									
Study Participants/Sample Collection	Individuals presenting to KCCR or MNIMR with suspected COVID-19 infection will be assessed by clinical staff and clinical specimens (e.g. nose, throat or nasopharyngeal swab, sputum or bronchoalveolar lavage collected for diagnostic testing.									
	Sera fromnSARS-Cov-2 positive and negative patients will be used to validate a proof of concept Immunoassay.									
Statistical Analysis	Data will be analyzed using software Statistical Packages for Social Science (SPSS) version 22.0. Sensitivity, specificity, positive predictive value, negat predictive value, and diagnostic accuracy will be calculated using standar formulas. Kappa and McNemar tests will be performed to determine to concordance and discordance between test assays and real-time RT-qPC based methods.									

1.0 Background and rationale for the study

In January 2020, the World Health Organization (WHO) declared a global health emergency over an outbreak of a new coronavirus (2019-nCoV), which originated in the Chinese city of Wuhan [1]. In February 2020, 2019-nCoV was renamed as severe acute respiratory syndrome coronavirus 2 (SARS-CoV-2) and the disease coronavirus disease (COVID-19) [2]. On 11 March 2020, the WHO characterised the COVID-19 outbreak as a pandemic [2], following alarming levels of infection spread and disease severity.

Nucleic acid testing (NAT) is the most reliable method to identify the causative agent (viral RNA), but these are expensive and usually require well-resourced laboratories. It is also not suitable for deployment outside a sophisticated laboratory environment with necessary equipment and skilled technicians (biosafety level 2 or above) [3]. In Ghana, there are national testing facilities in NMIMR and KCCR, with a combined capacity to process 4500 tests/day and now further regional testing is being established. The cost of testing (>\$10/test) in Ghana/Africa is not sustainable for long term testing. Detection of raised antibody titres is an alternative assay, but it first becomes useful later in the disease pathway and into recovery to identify people (including asymptomatic individuals) who have had the disease and are now showing immunity. This test is not sensitive early in infection. Together a NAT and immunoassay give a powerful tool for managing the spread of infection and 'herd immunity', as well as providing the best information for care of the patient. As such this study seeks to develop and evaluate new low-cost point of care (POC) and rapid throughput NAT and SARS-Cov-2 antibody titre tests in Ghana.

The advantages of the suitcase lab are:

A. Easy to be implemented in low resource settings.

B. Rapid time to result around 30 minutes including the extraction procedure.

The AfriDx consortium seeks to contribute to diagnosis of COVID-19 infection and patient management and public health preparedness in Africa, in response to the epidemic. It recognizes that Africa's demographics (1.3 billion population), its high prevalence of poor health and densely populated overcrowded urban areas present an enormous challenge to an under-resourced health service and may function to spread the virus suddenly and rapidly.

Figure 1: PATHPOD device and Suitcase lab for SARS-CoV-2 detection

2.0 Aim and study objectives

Aim

The aim of the project is to provide reliable diagnostic systems for the confirmation of the clinical diagnosis of COVID-19 in Africa from first infection through to recovery and immunity, with:

- RNA viral testing enabled for point of care (POC)
- Antibody titre testing for POC
- Sample to result time of less than one hour
- >90% sensitivity and specificity
- Compatibility for distributed production at low cost in Africa

Hypothesis

Test assays are as sensitive and specific as real-time RT-qPCR-based molecular methods.

Primary objective

To provide reliable diagnostic systems for the confirmation of the clinical diagnosis of COVID-19 in Africa from first infection through to recovery and immunity

Specific Objectives

The objectives are:

To use the front line testing facilities in NMIMR and KCCR, Ghana, as a testbed for a new POC nucleic acid diagnostic emerging from DTU (PATHPOD - detection of virus RNA), that is
 Protocol: AfriDx
 Page | 6
 Version: 1.0 20 December 2020

currently under clinical test in Europe and will be seeking Emergency Use Authorization (EUA) in the next 6 months.

Secondary Objective:

• To replace the BST and RT enzymes in the PATHPOD with BST and RT constructs designed by UCAM for low resource production in Africa and evaluate the AfriDX-RT-LAMP alongside the PATHPOD and standard RT-qPCR procedure

• To develop an Antibody Titre assay to proof of principle from a UCAM single-chain antibody (scFv) library and produce scFv constructs for low resource production of a lateral flow immunoassay (LFIA) in Africa (AfriMx).

• To evaluate combined batch testing as methodology adopted from normal veterinary protocols (but not widely used for human testing) and assess accuracy, cost and time benefits in epidemic testing pathways.

• To draft a plan to produce AfriDx in Africa for the African market, with outline analysis of socioeconomic and healthcare benefits.

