3.0 Study design

This study is a cross sectional experimental which involves the development and evaluation of two low cost point of care (POC) and rapid throughput NAT and SARS-Cov-2 antibody titre tests. This study has been organised into 9 works packages under the broad themes: Project management, development of point of care diagnostics, clinical study and field test, innovation and dissemination. The diagnostic performance of PATHPOD, a point of care viral detection system developed by DTU and adapted for SARS-Cov-2 viral assays will be evaluated with viral nucleic acid extracted from sputum, oral and nasal pharyngeal swabs. This evaluation will be conducted at KNUST, KCCR and NMIMR with assistance from DTU and TATAA using samples collected for both symptomatic patients and asymptomatic individuals, identified through contact tracing or through testing of healthcare workers. A comparative data with the currently used laboratorybased RT-qPCR will be obtained for the innovative RT-LAMP (PATHPOD) to produce information on sensitivity and specificity. After this initial evaluation of the PATHPOD, the low-cost systems (Boon-BST and Boon-RT production) developed at UCAM for expression and purification of the DNA polymerase Bst and a reverse transcriptase (RT), the enzymes used for the RT-LAMP assay in the PATHPOD system will be employed for local production these reagents. If successful, this locally produced reagents in Africa (AfriDx-RT-LAMP) will be tested on a subset of samples collected compare results to the existing PATHPOD system.

The high-affinity single-chain variable fragment (scFv) developed by UCAM (Proof of Concept Serological Test Development) for COVID-19 immunoassays will also be adapted in this study. The resulting proof of concept AfriMx system will be tested on a small number of serological samples that will be collected from individuals who test positive and negative for SARS-CoV-2. Boon-scFV production protocols and design principles for scFV immunoassays will be transferred and disseminated through training activities in Ghana (Training and Capacity Building).

Sample size and statistical analyses

NMIMR, KCCR are supporting the frontline of SARS-Cov-2 testing in Ghana using RT-qPCR. Their capacity is ~1500 tests/day. We envisaged a total of about 4000 tests from KNUST and KCCR.

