Data will be analyzed using software Statistical Packages for Social Sciences (SPSS) version 22.0. Sensitivity, specificity, positive predictive value, negative predictive value, and diagnostic accuracy will be calculated using standard formulas. Kappa and McNemar tests will be performed to determine the concordance and discordance between test assays and real-time RT-qPCR-based methods.

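### Parity with RT-qPCR cannot be tested when RT-qPCR is the only reference named, and the protocol does not say whether parity or the >90% aim governs

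*Protocol*

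**What the plan says.** Protocol Section 2.0 contains two performance statements. The list under Aim includes ">90% sensitivity and specificity", beside items such as time to result and low-cost production. A few lines later the Hypothesis reads "Test assays are as sensitive and specific as real-time RT-qPCR-based molecular methods". No margin is attached to it, and it is not limited to one of the assays.

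Section 3.0 gives the source of the accuracy figures: "A comparative data with the currently used laboratorybased RT-qPCR will be obtained for the innovative RT-LAMP (PATHPOD) to produce information on sensitivity and specificity". Section 5.0 repeats this. The analysis paragraph of Section 3.0 states "Sensitivity, specificity, positive predictive value, negative predictive value, and diagnostic accuracy will be calculated using standard formulas" and then "Kappa and McNemar tests will be performed to determine the concordance and discordance between test assays and real-time RT-qPCR-based methods". The Protocol Summary says the same. No composite reference, clinical follow-up or resolution of discrepant results is named.

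On size, Section 3.0 says "We envisaged a total of about 4000 tests from KNUST and KCCR". It describes the evaluation as covering "two low cost point of care (POC) and rapid throughput NAT and SARS-Cov-2 antibody titre tests", so the hypothesis as worded also takes in the antibody assay. Section 1.0 states that antibody testing lacks sensitivity early in infection.

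**The concern.** Sensitivity is the share of reference-positive samples that the assay calls positive, and specificity is the corresponding share of reference-negatives. If RT-qPCR is the reference, its own values are 100% and 100% whatever the data. A claim that another assay is as sensitive and as specific then reduces to a claim of no disagreement at all. It cannot be supported by degrees without a margin, and it cannot be turned round to show that the new assay is better.

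The only named significance test against RT-qPCR is McNemar. A reader may take a non-significant result as support for the hypothesis and a significant one as refutation. Either inference can be badly wrong. The >90% figure in the Aim is a different yardstick and can give a different verdict. With neither named as governing, the choice between them could be made after the results are known.

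**Working it through.** **Inputs from the protocol.** About 4000 tests (Section 3.0), the 90% figure (Section 2.0), and RT-qPCR as sole comparator (Sections 3.0 and 5.0). The 4000 comes with no alpha, power, margin, prevalence or expected accuracy. It cannot be reproduced, and it is not disputed here.

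**Assumptions, not in the protocol.** One RT-qPCR/assay pair per test, so N = 4000; RT-qPCR positivity from 2% to 30%; two-sided 95% exact (Clopper-Pearson) intervals.

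**Step 1: what McNemar tests.** Let FN be the RT-qPCR positives that the assay misses and FP the RT-qPCR negatives that it calls positive. McNemar tests FN = FP, that is, equal overall positivity. The exact p-value treats FN as binomial with FN + FP trials and probability 0.5.

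At 10% positivity there are 400 positives and 3600 negatives.

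- *Assay with sensitivity 60%, specificity 95.56%.* FN = 400 × 0.40 = 160 and FP = 3600 × 0.0444 = 160, so p = 1.0. Observed agreement is (240 + 3440)/4000 = 0.92. Chance agreement is (400² + 3600²)/4000² = 0.82. Kappa = (0.92 − 0.82)/(1 − 0.82) = 0.56. McNemar finds no difference, yet 40% of the positives are missed.
- *Assay with sensitivity 92%, specificity 92%.* FN = 400 × 0.08 = 32 and FP = 3600 × 0.08 = 288, so p is about 1e-52. McNemar rejects, yet both values exceed 90%.

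**Step 2: dependence on positivity.** Take an assay fixed at sensitivity 95%, specificity 99%.

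| Positivity | FN | FP | McNemar p |
|---|---|---|---|
| 10% | 20 | 36 | 0.044 |
| 20% | 40 | 32 | 0.41 |
| 30% | 60 | 28 | 0.0008 |

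The same assay is judged different, not different, and different again (in the opposite direction) solely because the case mix changes.

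**Step 3: the two yardsticks side by side.** At 95%/99% the assay clears the >90% aim on both measures. It is below the 100%/100% that RT-qPCR holds by construction, so parity fails. The protocol gives no order of precedence.

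**Step 4: can the 90% figure serve as a test?** Yes. Require the exact 95% lower limit for agreement with RT-qPCR positives to exceed 90%. The smallest passing count is the smallest r with P(X ≥ r) of at most 0.025 when the true value is 90%. The chance of passing is P(X ≥ r) at the assumed true value.

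| RT-qPCR positives (share of 4000) | Passing count | Chance of passing at true 95% |
|---|---|---|
| 80 (2%) | 78 | 23% |
| 200 (5%) | 189 | 70% |
| 400 (10%) | 372 | 97% |

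About 231 positives (217 needed to pass) give at least 80% power at a true sensitivity of 95%. Specificity is not the bottleneck: with 3600 negatives, an observed 99% has a lower limit of 98.6%, and even an observed 92% has one of 91.1%.

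**The case against.** Much can be said for the protocol. It never calls RT-qPCR a reference standard, and the hypothesis could be read as informal wording for good agreement, which kappa and McNemar are meant to describe. The >90% figure is one item in a list of project features, so a product target and a comparative hypothesis can coexist. A statistical analysis plan that is not shown may set the interval method and the decision rule.

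Part of this stands. That RT-qPCR is the reference is inferred, although nothing else in the protocol could play that role. A reader might infer that the two statements contradict each other. They do not strictly do so; they are unreconciled and can lead to different verdicts. A reader might also infer that the trial has no valid success rule. The protocol does not support that, because agreement above 90% with RT-qPCR is measurable and the missing bound may be set elsewhere. Nor does the protocol say that a point estimate above 90% means success, so the error rates of such a rule are not evidence about this plan.

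What does not stand is the rescue of the hypothesis. An analysis plan implements the protocol's hypothesis. It cannot make parity testable without replacing it, or without adding both an independent reference and a margin. McNemar answers another question, as Steps 1 and 2 show.

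**Conclusion.** The hypothesis is untestable as written, and the test placed beside it can point the wrong way: p = 1.0 for an assay that misses 40% of positives, and p of about 1e-52 for one above 90% on both measures. These figures rest on 4000 pairs and an assumed 10% positivity. The mechanism holds at any positivity, because McNemar sees only the balance of FN and FP. The logical part, that RT-qPCR scores 100% against itself, needs no assumption beyond its being the sole comparator.

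For the antibody assay the parity wording is also at odds with the protocol's own background statement about early infection.

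The finding goes no further than this: an unsuitable hypothesis, and two yardsticks without precedence. It does not show that the planned number of tests is wrong or that the >90% aim is unusable.

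**What to change.** Replace the hypothesis for PATHPOD with wording such as: PATHPOD meets its target if the lower limits of the exact two-sided 95% confidence intervals for positive and for negative percent agreement with RT-qPCR both exceed 90%. State that this governs the conclusion, and keep kappa and McNemar as descriptive only. The term percent agreement is preferable because no independent standard establishes that RT-qPCR is error-free.

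For AfriDx-RT-LAMP, which is to be run on a subset of unstated size, report the same estimates and intervals without a pass/fail rule. Do not apply the parity hypothesis to the antibody assay.

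The drafting cost is about one paragraph, to be settled before assay results are compared. The real cost is power. As Step 4 shows, an assay with true sensitivity 95% would more often than not fail the rule with 80 positives and would fail it 30% of the time with 200. If positives are few, the conclusion may be that the target was not shown. The expected number of RT-qPCR positives should therefore be stated alongside the rule.

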3.0 Study design

This study is a cross sectional experimental which involves the development and evaluation of two low cost point of care (POC) and rapid throughput NAT and SARS-Cov-2 antibody titre tests. This study has been organised into 9 works packages under the broad themes: Project management, development of point of care diagnostics, clinical study and field test, innovation and dissemination. The diagnostic performance of PATHPOD, a point of care viral detection system developed by DTU and adapted for SARS-Cov-2 viral assays will be evaluated with viral nucleic acid extracted from sputum, oral and nasal pharyngeal swabs. This evaluation will be conducted at KNUST, KCCR and NMIMR with assistance from DTU and TATAA using samples collected for both symptomatic patients and asymptomatic individuals, identified through contact tracing or through testing of healthcare workers. A comparative data with the currently used laboratorybased RT-qPCR will be obtained for the innovative RT-LAMP (PATHPOD) to produce information on sensitivity and specificity. After this initial evaluation of the PATHPOD, the low-cost systems (Boon-BST and Boon-RT production) developed at UCAM for expression and purification of the DNA polymerase Bst and a reverse transcriptase (RT), the enzymes used for the RT-LAMP assay in the PATHPOD system will be employed for local production these reagents. If successful, this locally produced reagents in Africa (AfriDx-RT-LAMP) will be tested on a subset of samples collected compare results to the existing PATHPOD system.

The high-affinity single-chain variable fragment (scFv) developed by UCAM (Proof of Concept Serological Test Development) for COVID-19 immunoassays will also be adapted in this study. The resulting proof of concept AfriMx system will be tested on a small number of serological samples that will be collected from individuals who test positive and negative for SARS-CoV-2. Boon-scFV production protocols and design principles for scFV immunoassays will be transferred and disseminated through training activities in Ghana (Training and Capacity Building).

Sample size and statistical analyses

NMIMR, KCCR are supporting the frontline of SARS-Cov-2 testing in Ghana using RT-qPCR. Their capacity is ~1500 tests/day. We envisaged a total of about 4000 tests from KNUST and KCCR.

Data will be analyzed using software Statistical Packages for Social Sciences (SPSS) version 22.0. Sensitivity, specificity, positive predictive value, negative predictive value, and diagnostic accuracy will be calculated using standard formulas. Kappa and McNemar tests will be performed to determine the concordance and discordance between test assays and real-time RT-qPCR-based methods.

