4.0 Research participants

Individuals suspected COVID-19 infection and presenting to KCCR, or KNUST and NMIMR with will be assessed by clinical staff and clinical specimens (e.g. nose, throat or nasopharyngeal swab, sputum or broncho-alveolar lavage collected for diagnostic testing upon giving their consent.

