5.0 Study procedures

The overall study will be performed, after obtaining regulatory and IRB approvals as applicable in the country and the participating institutions. According to the study design, the diagnostic performance of PATHPOD, a point of care viral detection system developed by DTU and adapted for SARS-Cov-2 viral assays will be evaluated with viral nucleic acid extracted from sputum, oral and nasal pharyngeal swabs. This evaluation will be conducted at KNUST, KCCR and NMIMR with assistance from DTU and TATAA using samples collected for both symptomatic patients and asymptomatic individuals, identified through contact tracing or through testing of healthcare

Protocol: AfriDx Version: 1.0 20 December 2020 workers. A comparative data with the currently used laboratory-based RT-qPCR will be obtained for the innovative RT-LAMP (PATHPOD) to produce information on sensitivity and specificity. After this initial evaluation of the PATHPOD, the low-cost systems (Boon-BST and Boon-RT production) developed at UCAM for expression and purification of the DNA polymerase Bst and a reverse transcriptase (RT), the enzymes used for the RT-LAMP assay in the PATHPOD system will be employed for local production of these reagents and testing. If successful, this locally produced reagents in Africa (AfriDx-RT-LAMP) will be tested on a subset of samples collected compare results to the existing PATHPOD system.

The high-affinity single-chain variable fragment (scFv) developed by UCAM (Proof of Concept Serological Test Development) for COVID-19 immunoassays will also be adapted in this study. The resulting proof of concept AfriMx system will be tested on a small number of serological samples that will be collected from individuals who test positive and negative for SARS-CoV-2. Boon-scFV production protocols and design principles for scFV immunoassays will be transferred and disseminated through training activities in Ghana (Training and Capacity Building).

Nucleic acid extraction and RT-LAMP

Viral RNA will be extracted and purified from swab using the heating method.

Virus lysis

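### PPV, NPV, overall accuracy and kappa are planned without a population attached, although they depend on the share of positives, which is set by sampling for AfriMx and by the recruitment mix for PATHPOD

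*Protocol*

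**What the plan says.** The statistical text in Protocol section 3.0 (under sample size and statistical analyses) is short. On accuracy: "Sensitivity, specificity, positive predictive value, negative predictive value, and diagnostic accuracy will be calculated using standard formulas". On agreement: "Kappa and McNemar tests will be performed to determine the concordance and discordance between test assays and real-time RT-qPCR-based methods". The accuracy sentence is general and names no assay. Neither sentence names a prevalence, a stratum or a population of use.

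The samples come from three differently composed sources:

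- **PATHPOD.** Section 5.0, like section 3.0, uses "samples collected for both symptomatic patients and asymptomatic individuals, identified through contact tracing or through testing of healthcare" workers. The shares of these groups are not fixed. Section 4.0 is narrower: "Individuals suspected COVID-19 infection and presenting to KCCR, or KNUST and NMIMR". Section 6.0 also describes suspected cases only.
- **AfriDx-RT-LAMP.** If local production succeeds, the reagents "will be tested on a subset of samples collected compare results to the existing PATHPOD system". No rule for choosing the subset is given.
- **AfriMx.** The immunoassay is tested on a "small number of serological samples that will be collected from individuals who test positive and negative for SARS-CoV-2". The ratio of positives to negatives is not given.

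The performance target, in section 2.0, is ">90% sensitivity and specificity". The hypothesis in the same section is also about sensitivity and specificity.

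**The concern.** PPV and NPV answer the question of what a result means for the person tested, and the answer depends on how common infection is among those tested. A raw 2x2 table gives a usable PPV only if its share of positives is that of a population someone cares about. For AfriMx the share follows from how many positive and negative sera are collected. For PATHPOD it follows from how many people arrive by each route, and the protocol describes that population in two ways (sections 3.0 and 5.0 against sections 4.0 and 6.0).

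The risk is in interpretation. Up to three assays, evaluated in differently composed samples, would each yield PPV, NPV and kappa values that look comparable and transferable but are neither. A reader planning use in another setting could take a PPV that belongs to the study's mix, or to a chosen case ratio, as a property of the test.

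**Working it through.** The protocol gives no figure to reproduce: no prevalence, no expected number of positives and no expected PPV or kappa.

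**Inputs.** Sensitivity (Se) and specificity (Sp) are set at 0.90, the edge of the target in section 2.0. Every positivity value p below is an assumption.

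**Formulas.**
- PPV = Se·p / [Se·p + (1−Sp)(1−p)]
- NPV = Sp(1−p) / [Sp(1−p) + (1−Se)p]
- Accuracy A = Se·p + Sp(1−p)
- Kappa = (A − Pe)/(1 − Pe), where Pe = T·p + (1−T)(1−p) and T = Se·p + (1−Sp)(1−p) is the share testing positive

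**Worked case, p = 0.10.** True positives 0.09, false positives 0.09, true negatives 0.81, false negatives 0.01. PPV = 0.09/0.18 = 0.500. NPV = 0.81/0.82 = 0.988. A = 0.90. Pe = 0.18×0.10 + 0.82×0.90 = 0.756. Kappa = (0.900 − 0.756)/0.244 = 0.590.

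**Same device, different share of positives (Se = Sp = 0.90).**

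| Assumed p | PPV | NPV | Accuracy | Kappa |
|---|---|---|---|---|
| 2% | 0.155 | 0.998 | 0.900 | 0.239 |
| 5% | 0.321 | 0.994 | 0.900 | 0.432 |
| 10% | 0.500 | 0.988 | 0.900 | 0.590 |
| 20% | 0.692 | 0.973 | 0.900 | 0.719 |
| 50% | 0.900 | 0.900 | 0.900 | 0.800 |

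**AfriMx.** Collecting one negative serum per positive gives p = 1/2 and a raw PPV of 0.90. Nine negatives per positive gives p = 1/10 and 0.50. Nineteen gives p = 1/20 and 0.32. The assay is the same in all three; only the collection ratio changes.

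**PATHPOD.** Suppose 20% positivity with symptoms and 3% without, both assumed. A symptomatic share of 25% gives p = 0.25×0.20 + 0.75×0.03 = 0.0725; shares of 50% and 75% give 0.115 and 0.1575. PPV is then 0.413, 0.539 and 0.627, and kappa 0.518, 0.620 and 0.680, for an unchanged device.

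**Accuracy.** When Se = Sp it does not move with p, as the table shows. When they differ it does: with Se 0.80 and Sp 0.98 it is 0.80×0.02 + 0.98×0.98 = 0.976 at p = 2%, and 0.80×0.50 + 0.98×0.50 = 0.890 at p = 50%.

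**The device also matters.** At p = 10%, Se = Sp of 0.90, 0.95 and 0.99 gives PPV 0.500, 0.679 and 0.917, and kappa 0.590, 0.764 and 0.946.

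**The case against.** The strongest reply is that nothing is decided on these measures. The target and the hypothesis are about sensitivity and specificity, and section 3.0 says the PATHPOD comparison is there to inform those two. That stands, and it limits the point to the reporting of secondary measures.

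A reader might infer that overall accuracy could hide a poor test. For example, Se 0.50 with Sp 0.99 at an assumed 5% positivity gives 0.05×0.50 + 0.95×0.99 = 0.966. The protocol does not support that worry: sensitivity is reported beside accuracy, and 0.50 would plainly miss the 90% target.

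A reader might also infer that all three assays use samples chosen by result. The protocol describes collection by result only for the AfriMx sera. The AfriDx-RT-LAMP subset has no stated rule, and the PATHPOD samples are mixed but not chosen by result, so their pooled PPV and NPV are valid for the study mix. Their limit is that they do not transfer.

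It can further be said that AfriMx is a small proof of concept, that the accuracy sentence does not expressly cover it, and that a statistical analysis plan, not shown here, could stratify or standardise. These replies soften the point but do not remove it. The protocol states the analysis in general terms, excludes no assay, and the natural reading of its reference to standard formulas is the raw 2x2 table.

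**Conclusion.** The concern holds in limited form. Raw PPV and NPV for AfriMx would estimate no population quantity, because the share of positives is set by collection. Pooled PPV, NPV and kappa for PATHPOD would describe only the study's own mix of recruits. Between assumed positivity of 5% and 50%, a device with Se = Sp = 0.90 moves from 0.32 to 0.90 in PPV and from 0.43 to 0.80 in kappa. Overall accuracy is affected only where sensitivity and specificity differ.

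It would be too strong to conclude that these measures reflect the share of positives instead of the device: at fixed positivity they respond clearly to the device as well. Nor is the 90% target undermined, since sensitivity and specificity do not depend algebraically on the share of positives. The sizes rest on assumed positivity values, because the protocol gives none; the direction does not.

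**What to change.** Amend the statistical text of Protocol section 3.0 as follows.

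(a) For AfriMx, and for the AfriDx-RT-LAMP subset if it is selected by result, do not calculate PPV, NPV or overall accuracy from the raw table. Report sensitivity and specificity, and derive PPV and NPV from them over a stated range of prevalence.

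(b) For PATHPOD, report PPV, NPV and kappa by recruitment route (symptomatic, contact, healthcare worker), and also give PPV and NPV over a stated range of prevalence.

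(c) State that conclusions rest on sensitivity and specificity, which already carry the target.

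The cost is a change of wording, one extra table, and wider intervals within strata than in the pooled sample. The recruitment route must be available for each PATHPOD sample. No new samples or tests are needed.
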